Effect of Post-Operative Anesthetics on Post-Operative Pain in Patients Receiving
Endodontic Treatment

NCT05338671

April 8, 2025

Study Protocol and Statistical Analysis Plan:

Participants: Participants were patients of the University of Washington School of Dentistry graduate endodontic clinic.

Exclusion and Inclusion Criteria: Exclusion criteria were the presence of any systemic diseases that precluded the administration of bupivacaine, lidocaine, or ibuprofen, pregnancy, and teeth that had periapical radiolucencies and a pulpal diagnosis of anything other than irreversible pulpitis. Inclusion criteria were healthy adults (18 years or older, ASA I or II), no contraindications to ibuprofen, mandibular posterior teeth with a pulpal diagnosis of irreversible pulpitis (symptomatic or asymptomatic, if pre-operative pain was present), and willing to undergo two-step nonsurgical root canal treatment.

Study Procedures: Patients were initially screened for inclusion and exclusion criteria at their consultation appointment at the University of Washington School of Dentistry graduate endodontic clinic. If the patient met the inclusion criteria, they were asked if they wanted to participate in the study. If they agreed to participate, the research consent forms were signed, and they were given a questionnaire prior to the start of their root canal treatment to rate the pain they were experiencing on a numerical rating scale. At the end of a root canal appointment, it is common to administer additional local anesthetic to keep the tooth numb for a period of time and in order to decrease the amount of post-operative pain a patient could experience even after the anesthetic wears off. However, there is no evidence that supports the use of one anesthetic solution over the other, which is what this study aims to find. Patients were randomized into either the Bupivacaine group (long-acting anesthetic) or Lidocaine (short-acting anesthetic) group. The patients were assigned a research number, which was used for the remainder of the study. The resident treating the patient reconfirmed the diagnosis of the tooth prior to the start of treatment and if the diagnosis changed (i.e.. if the tooth did not have pulpitis and the nerve was dead), the patient was not included in the study. Root canal treatment was initiated using routine root canal procedures, which includes local anesthetic to get the tooth numb and application of a dental dam for isolation. The root canal space was cleaned, and the inflamed nerve removed. An inter appointment medication was placed in the root canals and the root canal access (hole on the biting surface of the tooth) was restored with a temporary filling material to avoid food getting impacted into this space. Following this, the patient received the local anesthetic that they were randomly assigned to: 1 carpule (1.7 mL) of 0.5% Bupivacaine with 1:200,000 epinephrine (long-acting anesthetic), or 1 carpule (1.7 mL) of 2% Lidocaine with 1:100,000

epinephrine (short-acting anesthetic). The patient was handed the questionnaire (the one they used prior to the start of the appointment) and asked to rate their pain scale on a similar numerical scale at different time intervals after treatment (6, 12, 24, 48, 72 hours). This questionnaire/pain tracking form did not add any time to their root canal procedure, and took 5-10 minutes per day for the patient to fill out while at home in the 72 hours following treatment. The time and date were written on the questionnaire for each individual patient so they could remember to rate their pain at these intervals. The patients were also instructed to take 600 mg of Ibuprofen (Advil) every 6 hours for post-operative pain if needed and asked to document this (how many times a day, how many days) on the questionnaire. Patients were encouraged to track their post-operative pain levels. The patients were instructed to bring this questionnaire back with them when they came back to the clinic to get their root canal treatment completed. At the second treatment appointment, the questionnaire was collected from them and documented and the root canal treatment was completed at this appointment as it would be done for any patient not participating in the study.

Data Analysis: Data were analyzed using SigmaPlot (Grafiti LLC, Palo Alto, CA) for all statistical analyses. Intergroup comparisons were analyzed using a two-sample t-test, intragroup comparisons using a Wilcoxon signed-rank test, post-operative analgesic consumption comparisons using the Fisher Exact Test, and comparisons between male and female post-operative pain levels using the chi-square test.

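### Pain is compared between arms at five possible times with no primary time, summary measure, alpha or multiplicity adjustment stated; one unadjusted test per time would put the false-positive chance above 5% and as high as 23%.

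*Combined protocol and SAP*

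**What the plan says.** Under Study Procedures, the aim is given only in general terms: "there is no evidence that supports the use of one anesthetic solution over the other, which is what this study aims to find". Patients go to bupivacaine or lidocaine at random, and afterwards they are "asked to rate their pain scale on a similar numerical scale at different time intervals after treatment (6, 12, 24, 48, 72 hours". That gives five post-operative ratings per patient.

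The between-arm pain analysis is one clause under Data Analysis: "Intergroup comparisons were analyzed using a two-sample t-test". The same sentence adds "intragroup comparisons using a Wilcoxon signed-rank test, post-operative analgesic consumption comparisons using the Fisher Exact Test", and a chi-square comparison of men and women. The section names the software and the tests. It does not name a primary outcome, a primary time, a summary such as mean or peak pain, a repeated-measures model, a significance level, its sidedness or any adjustment for multiple tests. Nothing in the text suggests that this was blacked out or lost.

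**The concern.** A two-sample t-test uses one value per patient, and the trial collects five. The document does not say which value, or how many tests, decide whether one anesthetic is supported over the other. If a t-test was run at every time without adjustment, significance at any one of them could be taken as the answer. A reader holding only this document could not tell whether that result was the one meant to decide the question. At stake is the trial's main conclusion: a difference at one time out of five is weaker evidence than its unadjusted p-value suggests.

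**Working it through.** There is no stated alpha, power or sample size to reproduce, so the check is of error rates under stated assumptions.

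**Inputs**
- Number of post-operative ratings: 5 (Study Procedures).
- Test: two-sample t-test between two arms (Data Analysis).
- One test per time, two-sided 0.05 each, no adjustment: assumed.
- Correlation r between ratings at different times: not given. The range from 0 up to 1 is shown, with 0.5-0.8 as an assumed illustration.
- Error is calculated with no true difference at any time.

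**Unadjusted, r = 0.** 1 - 0.95^5 = 0.226.

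**Unadjusted, equal correlation r.** With c = 1.96 and u standard normal, the chance of at least one false difference is

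1 - E_u{[Phi((c - sqrt(r)u)/sqrt(1-r)) - Phi((-c - sqrt(r)u)/sqrt(1-r))]^5}.

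| r | Chance of at least one false difference |
|---|---|
| 0 | 22.6% |
| 0.5 | 18.3% |
| 0.8 | 12.7% |
| 0.95 | 8.5% |
| 0.99 | 6.5% |

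The limit as r approaches 1 is 5%.

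**Unadjusted, decaying correlation.** Ratings at 6 and 72 hours need not be as closely related as those at 6 and 12. With a first-order autoregressive pattern, simulation gives about 20% for an adjacent correlation of 0.5 and about 15% for 0.8. Taking both patterns together, 0.5-0.8 corresponds to about 13-20%.

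**Check with actual t-tests.** Simulations with an assumed 15 to 50 patients per arm and equal correlation give 22-23% at r = 0, 18-19% at 0.5 and about 13% at 0.8, so the normal approximation is adequate.

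**After Holm.** The smallest p-value must be below 0.05/5 = 0.01, a cut-off of 2.576. At r = 0 the error is 1 - 0.99^5 = 4.9%. The same integral with c = 2.576 gives 4.2% at 0.5, 3.0% at 0.8 and 1.9% at 0.95.

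**Power cost of Holm.** A test with 80% power at two-sided 0.05 has a standardised mean of 1.960 + 0.842 = 2.802. At Holm's first step its power is Phi(2.802 - 2.576) = Phi(0.226) = 0.59. That is the floor, reached when this time is the only one with an effect. Holm relaxes the threshold after each rejection: in simulation with 80% power at all five times, power per time is about 70% / 69% / 67% / 65% at r = 0 / 0.5 / 0.8 / 0.95.

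**The case against.** The strongest reply is that no error is documented. The plan does not say that a test was run at each time, that 0.05 was used, or that a difference at any one time would settle the question. A single t-test on a summary of the five ratings also fits the wording, and it would carry no inflation across times. This stands, and it makes every percentage above conditional. It does not remove the gap: the deciding comparison is unstated on any reading.

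A reader might infer three stronger things.

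- **That five unadjusted tests were certainly run, or that the trial's finding is a false positive.** The plural in the between-arm clause fits several tests but does not prove them, and the document reports no results.
- **That analgesic use is a further route to the conclusion, or that it must always rank second.** The plan lists "post-operative analgesic consumption comparisons using the Fisher Exact Test" without giving any order of outcomes. The title and rationale concern pain, so nothing shows that analgesic use was meant to answer the aim alone. Equally, an earlier record that made it primary should not be overridden.
- **That Holm always cuts 80% power to 59%.** That is the worst case only.

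**Conclusion.** The point holds in conditional form. It is certain that the document names no primary time, summary measure, alpha or multiplicity adjustment for five repeated pain ratings. If one two-sided 0.05 t-test was run per time, the chance of at least one false between-arm difference exceeds 5% and reaches at most about 23% for non-negative correlation. At an assumed correlation of 0.5-0.8 it is about 13-20%, the lower end coming from equal correlation and the upper end from decaying correlation. The figures cover only the five between-arm pain tests, not the within-group, analgesic or sex comparisons. The correction should be made: it is cheap and could change the conclusion. Confidence is medium because the number of tests actually run is unknown.

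**What to change.** State which between-arm pain comparison was made and at what alpha. Then:

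1. **Five tests run, and no dated record from before the data were seen names the primary comparison.** Apply Holm across the five between-arm pain p-values at two-sided 0.05. Report all five differences with unadjusted and adjusted p-values, and base the conclusion about the anesthetics on the adjusted results. Report analgesic use as secondary.
2. **Such a record exists.** State what it names (one pain time, several times, a summary, or analgesic use) and follow it. If several times are primary, keep Holm across them.
3. **A single summary of the ratings was tested.** State the summary; no adjustment across times is needed. Unless a dated record says otherwise, analgesic use is secondary here too.

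Label as post hoc any primary comparison chosen after the data were seen.

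Cost: a single primary comparison or a single summary needs about one added sentence. Holm needs no new data, only the p-values already computed. Its price is the loss of power at a single time shown above, and a conclusion that rests on one unadjusted time may not survive.

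### The between-arm pain comparison ignores the pre-operative pain score already collected; adjusting for it by ANCOVA could narrow the confidence interval

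*Combined protocol and SAP*

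**What the plan says.** The Data Analysis section is two sentences long. For pain between arms it gives one method: "Intergroup comparisons were analyzed using a two-sample t-test". No covariate, regression, ANCOVA or mixed model is named, and the text does not say whether the test is on raw post-operative scores or on change from baseline. The Wilcoxon signed-rank test is for comparisons within a group and does not adjust the comparison between arms.

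Study Procedures describes a baseline score. Patients were "given a questionnaire prior to the start of their root canal treatment to rate the pain they were experiencing", on a numerical rating scale. The canals were then cleaned, medicated and temporarily filled, and only after that: "Following this, the patient received the local anesthetic that they were randomly assigned to". The patient took the same form home and rated pain at 6, 12, 24, 48 and 72 hours.

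Sample size, alpha, power, SD, allocation ratio and the correlation between pre- and post-operative pain are not stated.

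**The concern.** The trial's stated aim is to compare the two anesthetic solutions, so the precision of that contrast matters. The plan collects a measurement of the same construct as the outcome, taken before the assigned anesthetic, and gives it no stated role in the comparison. Where pre- and post-operative pain are correlated, the unadjusted test leaves explainable variation in the error term and the interval for bupivacaine versus lidocaine is wider than it need be.

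This is a matter of efficiency. The t-test is not biased and its Type I error is not in question.

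**Working it through.** **Inputs from the documents.** Between-arm test: two-sample t-test, no covariate (Data Analysis). Baseline: pain score before treatment (Study Procedures). Outcome: pain score at five times up to 72 hours (Study Procedures). The plan has no power or sample-size figure to reproduce.

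**Assumptions.** t-test on raw post-operative scores; 1:1 allocation; two-sided 5% level; effect set so that the t-test has 80% power; ρ of 0, 0.2, 0.4 or 0.6; n per arm of 10, 20, 30 or 50.

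**Step 1: is the score a legitimate covariate?** The order is score, canal treatment, temporary filling, assigned anesthetic. The text does not say whether the score preceded randomization, but it preceded the assigned anesthetic and so cannot be an effect of it.

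**Step 2: large samples.** ANCOVA variance = (1 − ρ²) × t-test variance, so the CI-width ratio is √(1 − ρ²) and power is Φ((1.96 + 0.8416)/√(1 − ρ²) − 1.96). For ρ = 0.4: √0.84 = 0.917, and Φ(2.8016/0.9165 − 1.96) = Φ(1.097) = 0.864.

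**Step 3: small samples.** ANCOVA has 2n − 3 degrees of freedom, against 2n − 2 for the t-test. Chance baseline imbalance multiplies the variance by 1 + 1/(2n − 4). The CI-width ratio is therefore √(1 − ρ²) × f, where f = [t(0.975, 2n−3)/t(0.975, 2n−2)] × √(1 + 1/(2n−4)). For n = 20, f = (2.0262/2.0244) × √(37/36) = 1.015. Power uses the noncentral t with the same variance factor.

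| ρ | CI ratio, large n | CI ratio, 20 per arm | CI ratio, 10 per arm | Power, large n | Power, 20 per arm | Power, 10 per arm |
|---|---|---|---|---|---|---|
| 0 | 1.000 | 1.015 | 1.035 | 80% | 79% | 77% |
| 0.2 | 0.980 | 0.994 | 1.014 | 82% | 80% | 79% |
| 0.4 | 0.917 | 0.930 | 0.949 | 86% | 85% | 84% |
| 0.6 | 0.800 | 0.812 | 0.828 | 94% | 93% | 92% |

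The power columns apply only if ANCOVA is fixed before the data are analysed.

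**Step 4: break-even.** The ANCOVA interval is the narrower one when √(1 − ρ²) × f < 1, that is, when ρ > √(1 − 1/f²). This gives ρ above 0.258, 0.170, 0.135 and 0.103 at 10, 20, 30 and 50 per arm.

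**Step 5: simulation.** At 20 per arm (40,000 trials per setting) ANCOVA power was 0.786, 0.804, 0.853 and 0.933 for ρ = 0, 0.2, 0.4 and 0.6, matching the formula. With assumed whole-number 0–10 scores floored at zero, t-test power was 0.78 and ANCOVA power 0.771, 0.789, 0.834 and 0.911. Type I error was 4.7% to 5.3% for both tests in all runs.

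**Step 6: allocation.** With arm fractions p₁ and p₂, equal outcome SDs, slopes b₁ and b₂ in SD units, and pooled slope b = p₁b₁ + p₂b₂, the large-sample variance ratio to the t-test is Σ[(1 − 2b·bₖ + b²)/pₖ] / Σ(1/pₖ).

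| Allocation | Slopes (larger arm first if unequal) | Variance ratio |
|---|---|---|
| 1:1 | 0.4, 0.4 | 0.84 |
| 1:1 | 0.6, 0.2 | 0.84 |
| 2:1 | 0.4, 0.4 | 0.84 |
| 2:1 | 0.6, 0.2 | 0.91 |
| 2:1 | 0.4, 0 | 1.00 |
| 2:1 | 0.5, −0.5 | 1.08 |

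The gain can vanish or reverse only when allocation is unequal and the slopes differ strongly.

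**Step 7: if the t-test was on change scores.** With equal variances, the large-sample CI-width ratio of ANCOVA to the change-score test is √((1 + ρ)/2): 0.806 at ρ = 0.3 and 0.866 at ρ = 0.5. ANCOVA is again narrower, for any ρ below 1, but the table and break-even values above do not carry over.

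**The case against.** The strongest reply is that nothing here is an error: the comparison is valid, the gain cannot be sized, and the analysis appears to be finished.

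- **Low correlation.** The documents themselves give reasons to expect a low ρ. "The root canal space was cleaned, and the inflamed nerve removed", so the source of the pre-operative pain is treated. Ibuprofen is available "every 6 hours for post-operative pain if needed", which may blunt differences in later scores. Eligibility covers irreversible pulpitis "symptomatic or asymptomatic, if pre-operative pain was present", which may restrict the baseline range. Nor need ρ be the same at 6 hours as at 72. This stands as a limit on the likely gain. It does not remove the case: no minimum pain score is set, so baseline scores can still vary, and at ρ = 0 the loss is only about 1 power point at 20 per arm and about 3 at 10 per arm.
- **Timing.** "Data were analyzed using SigmaPlot" is in the past tense, as is the rest of the document. If the analysis is complete, an ANCOVA added now yields a supportive interval and no confirmatory power. This stands, and the fix is split accordingly.
- **Raw or change scores.** The plan does not say which were tested. That affects the figures but not the direction (Step 7).
- **Five time points.** ANCOVA at each time leaves the plan without a primary time point or a multiplicity rule. That is true of the existing t-test as well; ANCOVA neither causes nor worsens it.

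**Conclusion.** The concern holds. The only between-arm pain test named is unadjusted, although a suitable baseline covariate is already on the questionnaire. The cost is precision, not validity.

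On a raw-score reading with about 1:1 allocation, the change in CI width at 20 per arm runs from about 1.5% wider at ρ = 0 to 7% narrower at 0.4 and 19% narrower at 0.6. At 10 per arm it runs from 3.5% wider to 5% and 17% narrower. Every one of these figures rests on an assumed ρ and n. The downside is small and bounded when ρ is near zero; the upside is larger if ρ reaches about 0.4. Confidence that adjustment would help appreciably is moderate, because the clinical setting may well produce a low correlation.

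**What to change.** Add to Data Analysis:

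> At each of 6, 12, 24, 48 and 72 hours, the post-operative pain score is compared between arms by ANCOVA with the pre-operative score as covariate. Adjusted mean differences are reported with 95% confidence intervals.

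A single repeated-measures model with arm, time, arm-by-time, baseline and baseline-by-time is an acceptable alternative.

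- If the data have not been analysed, make this the main between-arm analysis and keep the t-test as a sensitivity analysis.
- If they have been analysed, keep the t-test as the planned result and report ANCOVA as supportive, labelled as added after the original plan.
- In both cases report the allocation ratio and the observed correlation of pre- and post-operative scores, and state whether the t-test uses raw or change scores.

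The post-operative scale is described only as similar to the pre-operative one. ANCOVA does not need identical scales; a change score would.

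The cost is one degree of freedom per ANCOVA, a sentence or two of text and a little analysis time. No new data or patients are needed.

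### The between-arm analysis of five repeated pain ratings is an unadjusted two-sample t-test; read as hour-by-hour tests, it ignores the pre-operative rating and drops patients with a blank at that hour

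*Combined protocol and SAP*

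**What the plan says.** Study Procedures describes a pain rating before treatment and five more "at different time intervals after treatment (6, 12, 24, 48, 72 hours"). The later ratings are made by the patient alone, on a paper form meant "for the patient to fill out while at home in the 72 hours following treatment". The reminder is on the paper itself: "The time and date were written on the questionnaire for each individual patient so they could remember to rate their pain". The pre-operative rating is on the same sheet: "The patient was handed the questionnaire (the one they used prior to the start of the appointment"). Patients are "instructed to bring this questionnaire back with them when they came back to the clinic", so every rating reaches the file by one route.

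Data Analysis gives one clause to the comparison between arms: "Intergroup comparisons were analyzed using a two-sample t-test". Within arms the plan is "intragroup comparisons using a Wilcoxon signed-rank test", which compares two measurements at a time. The section names no primary hour, per-patient summary, covariate, repeated-measures model or treatment of missed ratings. The document gives no sample size, standard deviation, correlation or missing-rating rate.

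**The concern.** The outcome is a repeated measure with a baseline, while the named test takes one number per patient. Applied at 24 hours, it compares the patients who wrote something at 24 hours. A patient who skipped that entry but filled in 12 and 48 hours contributes nothing, and no patient's pre-operative score is used.

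Two things are at stake. One is precision: collected information that predicts the outcome is left out. The other is bias: diary entries made at home without supervision may well stop once pain has settled. If that happens more often in the arm with less pain, the remaining ratings in that arm are the more painful ones and the arms look more alike than they are.

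**Working it through.** **Plan's own figure.** There is none to reproduce. Everything below is illustration on assumed inputs.

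**Inputs.** From the documents: five post-operative ratings, one pre-operative rating, two arms. Assumed: equal variances; correlation 0.4 between the pre-operative and each post-operative rating; correlation 0.6 to 0.75 between post-operative ratings, either equal for all pairs or holding for neighbouring hours and decaying with distance (AR(1)); each rating missed independently with probability m.

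**Step 1, the covariate.** Adjusting for a baseline with correlation r multiplies the variance by 1 − r² = 1 − 0.4² = 0.84, a 16% reduction. This does not depend on missing data.

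**Step 2, the repeated-measures step, with the covariate in both methods.** After adjustment, the correlation between post-operative ratings is (ρ − 0.16)/(1 − 0.16): 0.524 for ρ = 0.6 and 0.702 for ρ = 0.75. The hour-by-hour comparison keeps a share 1 − m of patients. The joint model keeps 1/[I⁻¹]ₜₜ, where I is the inverse correlation matrix of the observed ratings, averaged over all 32 patterns of missed entries.

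| m | Structure | Share kept, hour by hour | Share kept, joint model | Variance ratio |
|---|---|---|---|---|
| 0 | any | 1.00 | 1.00 | 1.00 |
| 10% | equal | 0.90 | 0.939-0.960 | 1.04-1.07 |
| 10% | decaying | 0.90 | 0.924-0.962 | 1.03-1.07 |
| 20% | equal | 0.80 | 0.870-0.912 | 1.09-1.14 |
| 20% | decaying | 0.80 | 0.840-0.913 | 1.05-1.14 |

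The ratio is the hour-by-hour variance divided by the joint-model variance, so hour by hour it is 3-7% larger at 10% missed and 5-14% larger at 20% missed. Stated as a reduction, 1 − 1/1.14 is about 12% at most. The low ends are the decaying structure at 6 and 72 hours, where a rating has a neighbour on one side only.

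**Step 3, both steps together, against the unadjusted t-test.** The reduction is 1 − 0.84/ratio: 16% with complete forms, about 18-21% at 10% missed (ratios 1.027 to 1.069) and about 20-26% at 20% missed (ratios 1.050 to 1.141).

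**Step 4, ratings that stop when pain is low.** Suppose both arms follow one rule: the 24-hour rating is skipped when the 12-hour rating is below a fixed low cut. The true arm difference is 0.50 SD at both hours. Put the cut where 20% are missing in the lower-pain arm; about 9% are then missing in the other. The mean of the remaining 24-hour ratings rises by ρ·λ, with λ = φ(a)/(1 − Φ(a)), where a is the cut in SD units from that arm's mean. For the lower-pain arm a = −0.842 and λ = 0.350; for the other a = −1.342 and λ = 0.178. The apparent difference is 0.50 + ρ(0.178 − 0.350) = 0.50 − 0.172ρ:

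- ρ = 0.5: 0.41 SD
- ρ = 0.7: 0.38 SD

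Simulation reproduces both values. Using the 12-hour rating in the analysis returns 0.50 SD.

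A second simulation, with 30 per arm, a 0-10 scale floored at 0, and missing ratings rising from about 10% at 12 hours to 40% at 72 hours, gave a milder result. The t-test understated differences of 0.66-0.91 points by 3-8%. The model was within about 5% through 48 hours but overstated by 7-9% at 72 hours.

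**Step 5, whole forms lost.** If 10% or 20% of forms never come back, the share kept is 0.90 or 0.80 under either method. The model recovers nothing.

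**The case against.** The text does not say that the t-tests are run hour by hour. They could be on change from baseline or on a per-patient summary. No rule for blanks is stated, so dropping them is the test's default behaviour, not the sponsor's declared policy. This stands, and it is why the point is conditional. It does not dispose of it. A change score does use the baseline, but at correlation 0.4 with equal SDs its variance is 2(1 − 0.4) = 1.20, against 1.00 unadjusted and 0.84 adjusted. A summary over hours still needs a rule when one component is blank.

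No missing rate is reported. With complete forms the repeated-measures step adds nothing, and only the covariate gain remains. The written due times may have kept blanks rare. With one sheet carried home and back, whole-form loss may be the main route, and the model cannot help there. All of this stands.

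A per-hour t-test in a randomized comparison is valid when ratings are missed completely at random. A reader might infer that the named test is wrong, or that the results are biased. The documents support neither: they show no pattern of missing ratings at all. A reader might also expect the joint model to win back nearly all of the precision lost at 20% missed, where the ceiling is 1/0.80 − 1 = 25%. The calculation gives at most about 14%.

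The bias argument cuts both ways. The size depends on the stopping rule, and in the floored simulation the model itself over-corrected at 72 hours.

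**Conclusion.** The concern holds in a limited form. Six ratings per patient are planned, and the only between-arm method named is an unadjusted two-sample test. On its natural reading that test leaves the pre-operative score unused and discards a patient's other ratings when one hour is blank.

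The surer gain is the covariate: about 16% lower variance if the correlation is 0.4. The repeated-measures step is worth less, and only if single ratings were skipped. Protection against stop-when-low missingness is a further reason, but whether that occurred is unknown. A reader might take the plan to state that only ratings present at a given hour are used; it states no such rule. This is a worthwhile improvement at low cost, not a flaw that invalidates the comparison. Confidence in its size is moderate, because every quantity rests on assumed correlations and missing rates.

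**What to change.** Make the main between-arm analysis one linear mixed model for repeated measures:

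- **Response:** ratings at 6, 12, 24, 48 and 72 hours.
- **Fixed effects:** arm, hour, arm-by-hour, pre-operative rating, pre-operative rating-by-hour.
- **Covariance:** unstructured within patient, with a named simpler structure if it does not converge.
- **Patients:** every randomized patient with at least one post-operative rating, with a stated rule for a blank pre-operative entry.
- **Report:** arm difference with 95% CI at each hour; number of ratings by arm and hour; unreturned forms by arm.
- **Supporting analysis:** the two-sample t-test, with the hour or summary it is applied to written down.

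The cost is a few lines of text and one model run, possibly in software other than SigmaPlot; no new patients or data are needed. Data Analysis is written in the past tense, so if results have been seen, this should be labelled as a re-analysis chosen afterwards. Three limits should be stated with it: the model assumes that missed ratings are explained by observed ones, it may over-correct at 72 hours when many scores are zero, and it cannot recover forms that never came back.

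### Within-arm Wilcoxon tests cannot show which solution is better; conclusions should rest on the between-arm difference adjusted for pre-operative pain

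*Combined protocol and SAP*

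**What the plan says.** The Study Procedures section states the question as one between two solutions: "there is no evidence that supports the use of one anesthetic solution over the other, which is what this study aims to find". The design matches it: "Patients were randomized into either the Bupivacaine group (long-acting anesthetic) or Lidocaine (short-acting anesthetic) group". Both arms are active, and no arm goes without a post-operative injection.

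Pain is first rated before treatment: "they were given a questionnaire prior to the start of their root canal treatment to rate the pain they were experiencing". It is rated again at 6, 12, 24, 48 and 72 hours. Between the first rating and all later ones, the same thing is done to every patient: "The root canal space was cleaned, and the inflamed nerve removed". Patients in both arms may also take ibuprofen as needed.

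The Data Analysis section then names two analyses of pain over the whole follow-up. One is between arms: "Intergroup comparisons were analyzed using a two-sample t-test". The other is within arms: "intragroup comparisons using a Wilcoxon signed-rank test". No adjustment for the pre-operative rating is mentioned. The section does not say which ratings the Wilcoxon test pairs, what it is for, or which of the two analyses carries the conclusion.

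**The concern.** Take the Wilcoxon test as comparing the pre-operative rating with a later one. Its null hypothesis is that pain did not change in that arm. That null is expected to be false in both arms whichever carpule was given, because the inflamed nerve is removed in all patients and ibuprofen is available to all. Pre-operative pain also appears in the entry criteria, so regression to the mean can lower later scores as well. With no arm lacking an injection, the within-arm change cannot be divided into an anesthetic part and a recovery part.

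What is at stake is how the results are read. If bupivacaine shows p < 0.05 and lidocaine does not, it is easy to write that one solution reduced pain and the other did not. That is a claim about a difference between arms, and no within-arm test examines that difference. Adjusting the p-values for multiplicity would not help: an adjusted test of no change in this arm still says nothing about one solution against the other.

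**Working it through.** **Inputs.** From the document: two randomized arms, one pre-operative and five post-operative ratings, within-arm Wilcoxon signed-rank test, between-arm two-sample t-test. Not in the document, so assumed: two-sided 0.05, a 0–10 scale, baseline mean 5, 15 to 50 patients per arm, falls of 0 to 3 points, and the spread and correlation given below. The true fall is the same in both arms throughout, so any apparent arm difference is false. The plan has no figure of its own to reproduce.

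**Step 1, formula.** If each within-arm test has power p and the arms are independent, the chance that exactly one arm is significant is p(1−p) + (1−p)p = 2p(1−p).

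- p = 0.05: 2 × 0.05 × 0.95 = 9.5%
- p = 0.20: 2 × 0.20 × 0.80 = 32%
- p = 0.50: 2 × 0.50 × 0.50 = 50% (the maximum)
- p = 0.80: 2 × 0.80 × 0.20 = 32%
- p = 0.95: 2 × 0.95 × 0.05 = 9.5%

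The split is common when within-arm power is middling and rare when it is very high.

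**Step 2, simulation at one time.** Rounded scores held within 0–10, baseline SD 2.2, later score = (5 − fall) + 0.5 × (baseline − 5) + error with SD 2.2, 2,000 trials per cell. Percentage of trials with exactly one arm significant:

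| Per arm | 0.5-point fall | 1 point | 1.5 points | 2 points | 3 points |
|---|---|---|---|---|---|
| 15 | 19 | 41 | 50 | 32 | 3 |
| 20 | 23 | 48 | 42 | 16 | 0.2 |
| 30 | 29 | 50 | 23 | 3 | 0 |
| 50 | 41 | 34 | 3 | 0 | 0 |

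The between-arm t-test on the same data rejected in 4–6% of trials in every cell.

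**Step 3, other assumed inputs.** With SD 2.5, pre/post correlation 0.4 and 15 to 40 per arm, the split occurs in 37–48% of trials for a 1-point fall, 17–50% for 1.5 points and 0–6% for 3 points. With a 3-point fall both arms are significant in 93–100% of trials, so the tests then say nothing about a difference.

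**Step 4, any of five times.** This assumes that each post-operative rating is paired with baseline, with SD 2.5 and correlation 0.4 as in step 3. With correlation 0.7 among the post-operative ratings (300 trials per cell), the chance of at least one split at 15, 30 and 40 per arm is:

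- falls growing from 0.5 to 2.5 points: 84%, 72%, 63%
- falls growing from 2 to 4 points: 45%, 8%, 2%
- falls growing from 3 to 4.8 points: 7%, 0%, 0%

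A repeat gave 73–87%, 2–46% and 0–8% for the three paths. The fair comparator is not 5% but the chance that any of five unadjusted t-tests is significant, about 14–19% (19–24% under other assumed paths). So the split is several times more frequent than a false t-test result when falls are small, and less frequent when falls are large.

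**Step 5, gain from adjustment.** In theory, adjusting for baseline multiplies the standard error of the arm difference by √(1 − r²). At an assumed r = 0.4 this is √(1 − 0.16) = 0.917, about 8% smaller. With rounded scores held within 0–10 in small arms, simulation gives about 6–7% smaller.

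**The case against.** The strongest reply is that the faulty inference is not in the document. The section names a direct arm comparison before the within-arm tests, and nothing says that Wilcoxon results will be compared across arms. A within-arm test validly asks whether pain changed in that arm, a reasonable descriptive question after root canal treatment. All of this stands.

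A reader might infer four stronger things, and the documents support none of them.

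- *The plan judges the solutions by their within-arm p-values.* It assigns those tests no role at all. The fault is the missing statement.
- *The Wilcoxon tests measure recovery and not the anesthetic.* Within-arm change includes any anesthetic effect. It cannot separate that effect from recovery.
- *There are ten tests.* 2 arms × 5 times = 10 assumes that every post-operative rating is paired with baseline. The plan does not name the pairs.
- *The false-contrast rate is always far above 5%.* It is 0–6% at a single time for a 3-point fall. If removing the nerve produces large falls, the misleading pattern will be rare.

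It is also fair to say that deleting the within-arm tests is not required. Labelling them descriptive and naming the pairs removes the risk equally well.

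What the reply leaves untouched is that the t-test is unadjusted although a pre-operative rating exists for this purpose, and that nothing guards against reading the two sets of p-values together.

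**Conclusion.** The concern holds as a risk of misreading, joined to an avoidable loss of precision. That within-arm change cannot isolate the anesthetic follows from the design and needs no assumed figure beyond the pre-to-post pairing. Hence significance in one arm only is not evidence that the arms differ.

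The size of the risk is uncertain and should be quoted only as a range. With identical arms of 15 to 40 patients it is about 17–50% at one time for falls of 1 to 1.5 points and 0–6% for 3 points. Over five times it is anywhere from about 0% to 87% depending on the falls, against about 14–19% for any of five unadjusted t-tests. These figures rest on an assumed scale, spread, correlation and sample size. The precision gain from adjustment, about 6–7% in standard error, likewise assumes a correlation of 0.4.

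**What to change.** Replace the unadjusted two-sample t-test with an analysis of covariance at each time: post-operative pain on arm, with the pre-operative rating as covariate. Report the bupivacaine-minus-lidocaine difference with its 95% CI, and base every conclusion about the solutions on it.

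Present within-arm change descriptively, as a mean or median with a 95% CI at each time. If the Wilcoxon tests are kept, label them descriptive and name the pairs. State that no conclusion about the solutions is drawn from within-arm change.

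The section is written in the past tense, so if results have already been reported, check that no statement about the solutions rests on significance in one arm and not the other.

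The cost is slightly more analysis work and a few lines of text. The pre-operative rating was already collected, so no new data are needed. This change does not settle how five times are to be handled together; that is a separate question.
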